## 1 Introduction

Benign prostatic hyperplasia (BPH) is the most common benign neoplasm in men, with more than 50% of men in their sixties and as many as 90% in their seventies and eighties having some symptoms of BPH. As life expectancy increases, so does the occurrence of BPH. In the United States in 2000, there were 4.5 million visits to physicians for BPH with a direct cost of \$1.1 billion.

Medical treatment is usually the first line therapy for lower urinary tract symptoms (LUTS) due to BPH. The two main categories of medications for management of BPH are alpha blockers and 5 $\alpha$ -reductase inhibitors. Alpha blockers ( $\alpha$ 1-adrenergic receptor antagonists) are the most common choice for initial therapy. Patients who cannot tolerate these drugs or are refractory to treatment typically receive surgery or a minimally invasive therapy. In general, transurethral resection of the prostate (TURP) is still considered the gold standard of prostate interventions for patients who require a procedure. The procedure involves removing part of the prostate through the urethra with a resectoscope. There are also a number of less invasive methods for reducing prostate size, including radiofrequency, microwave and laser therapies. All of these treatment methods involve introducing energy into the body and urethral access and manipulation. All these technologies have the same objective—to remove prostate tissue to relieve constriction of the urethra or bladder outlet obstruction and reduce symptoms of LUTS. They produce outcomes similar to TURP, although there is not as much data on long term effectiveness as there is for surgery. The challenge for developing new methods of treating symptomatic BPH is to reduce hyperplastic tissue and achieve good long-term control of LUTS while reducing adverse events and negative impacts on quality of life, such as ejaculatory disorders.

Embolization of prostate arteries has been used for many years to control serious bleeding after biopsy or prostatectomy. The first published case in which it was recognized that embolization could have a therapeutic effect on benign prostatic hyperplasia (BPH) was by DeMeritt and colleagues. Prostate artery embolization (PAE) is an emerging therapy for LUTS associated with BPH, and has been demonstrated to reduce symptom burden, improve urodynamic measures, and decrease prostate size. On April 16, 2013 Embosphere Microspheres received the CE mark for the indication of embolization of the prostate gland for relief of symptoms related to benign prostatic hyperplasia, and on June 21, 2017 Merit Medical Systems, Inc received 513(f)(2) (de novo) classification from the FDA to expand the indication for Embosphere Microspheres to include prostatic artery embolization (PAE) for symptomatic benign prostatic hyperplasia (BPH).

The indication was granted based on the outcomes of published and unpublished data from 286 patients. The cohort is typical of the patient population treated for symptomatic benign prostatic hyperplasia. Mean age at baseline was  $67.7 \pm 9.7$ , lower urinary tract symptoms were severe as reflected in a mean International Prostate Symptom Score (IPSS) of  $21.5 \pm 6.8$ , and mean quality of life (QOL) score from the IPSS questionnaire was  $4.8 \pm 0.9$  ("mostly dissatisfied" to "unhappy"). Bilateral prostate embolization was achieved in 254 patients (88.9%), despite including 32 patients over the age of 80 and 54 with indwelling catheters at baseline for management of acute urinary retention. Mean symptom scores improved significantly compared to pretreatment values at every follow up interval. Mean IPSS scores improved from  $21.5 \pm 6.8$  at baseline to  $6.3 \pm 5.8$  ( $<0.0001$ ) and  $6.2 \pm 5.8$  ( $<0.0001$ ) at the 1-

3 month and 9-16-month follow-ups respectively. A reduction of IPSS score by at least 3 points was achieved at 9-16 months in 97% of patients, and 90% dropped by at least 1 symptom category.

The reduction of LUTS reflected in the IPSS changes affected mean quality of life. Mean QOL scores improved significantly from  $4.8 \pm 0.9$  ("mostly dissatisfied" to "unhappy") pre-embolization to  $1.4 \pm 1.2$  ( $<0.0001$ ) and  $1.4 \pm 1.1$  ( $<0.0001$ ; "pleased"/ "mostly satisfied") at the 1-3 month and 9-16-month follow-ups respectively.

## **2 Study Rationale**

Prostatic artery embolization with Embosphere Microspheres is a relatively new procedure. The goal of this post market study is to evaluate long-term safety and effectiveness in a 'real world' setting.

## **3 Study Objectives**

### **3.1 Primary Objective:**

Evaluate the long-term effectiveness of prostatic artery embolization (PAE) with Embosphere Microspheres as assessed by the International Prostate Symptom Score (IPSS) for those subjects who are eligible to complete a baseline IPSS for comparative purposes.

### **3.2 Secondary Objectives:**

- Evaluate IPSS and QoL after discontinuation of indwelling bladder catheter (IBC) post PAE
- Evaluation of device-related adverse events
- Evaluation of procedure-related adverse events
- Evaluate frequency of indwelling bladder catheter (IBC) removal post PAE
- Technical Success
  - Successful embolization of treated prostate gland
- Evaluation of additional treatments for refractory or recurrent LUTS due to BPH post PAE
- Evaluation of change from baseline in erectile function at 12 months post PAE using the Sexual Health Inventory for Men (SHIM). 12-16

### **3.3 Exploratory Objectives:**

If sufficient data is available, additional exploratory analyses will also be conducted. These may include, but are not limited to:

- Comparison of safety and effectiveness outcomes from patients treated with Embosphere Microspheres 100-300 $\mu$  vs 300-500 $\mu$
- Comparison of procedure time for patients embolized with radial vs femoral access
- Comparison of safety and effectiveness outcomes of embolizations that were/were not performed using the PErFecTED technique
- Comparison of effectiveness outcomes of bilateral vs unilateral embolizations
- Multivariate analyses to determine factors correlated to better effectiveness outcomes
- Evaluation of change from baseline prostate size at any time point post PAE

## 4 Study Design

This is a prospective, open label post market study to evaluate the long-term safety and effectiveness of PAE using Embosphere Microspheres. Up to 500 patients with LUTS due to BPH will be enrolled in this single arm post market study. All patients at sites who meet eligibility criteria will be offered participation. Long term effectiveness of PAE on LUTS will be evaluated by IPSS score at baseline, 3 months, 12 months, and 24 months. Note: All subjects will be asked to complete the IPSS. However, study subjects who have an indwelling bladder catheter will not be required to complete the IPSS; the IPSS questions may not be relevant to subjects with an indwelling bladder catheter. Safety will be assessed by evaluating device and procedure-related adverse events at the same time points, plus at 4 weeks following embolization. Erectile function will be assessed at baseline and 12 months by SHIM score. Additional treatments for refractory or recurrent LUTS due to BPH post prostatic artery embolization will also be recorded.

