## **8 Statistical Considerations**

### **8.1 Endpoint Definitions**

#### **8.1.1 Primary Endpoints**

The primary endpoint is the IPSS at 12 months.

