### 8.4.2 Evaluable Analysis Set (EAS)

Includes FAS patients where there are no significant deviations (e.g. not meeting the inclusion/exclusion criteria) from the protocol that did not have an indwelling catheter at the end of the procedure.

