## 18 Safety Medical Monitor

An independent safety medical monitor shall be responsible for systemic review and adjudication of specified events (e.g., all treatment-related adverse events and all deaths) . At a minimum, assess the reported event with the associated documented risks of device, vascular embolization, and PAE treatment.

Potential risk for Embosphere Microspheres:

- Immune reaction in patients who are hypersensitive to collagen or gelatin (careful consideration should be given prior to using this product in patients who are suspected to be allergic to injections containing gelatin stabilizers)

Potential risk for vascular embolization:

- Paralysis resulting from untargeted embolization or ischemic injury from adjacent tissue edema
- Undesirable reflux or passage of Embosphere Microspheres into normal arteries adjacent to the targeted lesion or through the lesion into other arteries or arterial beds, such as the internal carotid artery, pulmonary, or coronary circulations
- Pulmonary embolism
- Ischemia at an undesirable location, including ischemic stroke, ischemic infarction (including myocardial infarction), and tissue necrosis
- Capillary bed occlusion and tissue damage
- Vessel or lesion rupture and hemorrhage
- Vasospasm
- Recanalization
- Foreign body reactions necessitating medical intervention
- Infection
- Complications related to catheterization (e.g., hematoma at the site of entry, clot formation at the tip of the catheter and subsequent dislodgment, and nerve and/or circulatory injuries, which may result in leg injury)
- Allergic reaction to medications (e.g., analgesics)
- Allergic reaction o contrast media or embolic material
- Pain and/or rash, possibly delayed form the time of embolization
- Death
- Blindness, hearing loss, loss of smell, and/or paralysis

PAE specific potential complications:

- Non-targeted embolization of the rectum, bladder, scrotum, penis, or other areas
- The most frequent post-procedure complication includes “Post-PAE Syndrome,” which includes nausea, vomiting, fever, pelvic pain, burning sensation, dysuria, and frequent or urgent urination
- Skin burn (radiation exposure) from prolonged fluoroscopy time
- Blood in urine, semen, or stool
- Bladder spasm
- Hematoma at the catheter site
- Urinary tract infection
- Urinary retention
- Constipation

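### The IPSS analyses ignore catheter status at follow-up, so a man catheterised at 12 months contributes either a score of doubtful validity or an imputed average improvement

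*Combined protocol and SAP*

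**What the plan says.** - **Who completes the form.** Section 4 (Study Design): "All subjects will be asked to complete the IPSS. However, study subjects who have an indwelling bladder catheter will not be required to complete" the form. The reason given is that "the IPSS questions may not be relevant to subjects with an indwelling bladder catheter". The form is optional for these men. Nothing bars, voids or flags a score that one of them returns.
- **Who is compared.** Section 3.1 limits the primary objective by baseline status only: "for those subjects who are eligible to complete a baseline IPSS for comparative purposes".
- **Endpoint.** Section 8.1.1: "The primary endpoint is the IPSS at 12 months".
- **Analysis set.** Section 8.4.1 takes efficacy endpoints off the Full Analysis Set (FAS), which leaves the Evaluable Analysis Set (EAS). Section 8.4.2 limits the EAS to men "that did not have an indwelling catheter at the end of the procedure" and without significant protocol deviations.
- **Data collected.** Section 6.4 records changes in catheter use at 3, 12 and 24 months, the same visits as the IPSS.
- **Missing IPSS.** Section 8.5.2.1 fills a missing score with an age-specific average for the visit. The mixed model in 8.5.3.1 leaves missing scores missing, but one of its sensitivity analyses uses the same kind of average.
- **Foreseen event.** Section 18 lists "Urinary retention" among the complications specific to PAE.

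**The concern.** The plan itself doubts the IPSS in a man with an indwelling catheter, and it acts on that doubt at one moment only, the end of the procedure. Catheter status on the day of a follow-up questionnaire plays no part in the analysis. A man who leaves the procedure without a catheter, is catheterised later and is still catheterised at 12 months remains in the efficacy set. He has a poor functional outcome, but neither route through the plan records it as one. A returned form enters as an ordinary score, and a blank form is replaced by the average of men of similar age.

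The primary result is a single-arm mean change with a confidence interval. An error of this kind shifts the mean. The interval does not reveal it, more patients do not reduce it, and no control arm offsets it.

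**Working it through.** **Step 1. Does any other rule close the gap?**
- Section 3.1 conditions on a baseline IPSS, not on status at follow-up.
- Section 7 discontinues men who have a non-PAE BPH procedure. Catheterisation is not named there.
- Section 8.5.3.7 reports catheter removal among men who had a catheter during the procedure. Men catheterised later are outside it.
- Section 3.2 includes an objective on IPSS after catheter discontinuation. This links the score to catheter status but sets no rule for a score given while a catheter is in place.
- Section 8.5.2.1 also plans an analysis without the missing data. Dropping these men gives the mean of the remaining men, which is close to what average imputation gives, so it does not show the effect.

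No rule applies.

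**Step 2. Inputs for the blank-form route.**
- Baseline IPSS 21.5 and IPSS at 9–16 months 6.2: background cohort, section 1.
- Precision target ±1 unit: sections 8.2 and 8.3.
- SD 8.5, 10% missing, up to 500 patients: section 8.3.
- p, the share of analysed men who are catheterised at 12 months and leave the form blank: not in the documents. I assume 1% to 5%. The 54 of 286 men with catheters in section 1 (18.9%) are a baseline figure and do not supply p.
- Fair value for such a man: no change from baseline (assumption).

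**Step 3. Credit per man.** Imputed change = 6.2 − 21.5 = −15.3, against a fair value of 0.

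**Step 4. Shift in the mean.** Shift = p × 15.3, in favour of PAE.

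| p (assumed) | Shift in mean change (points) |
|---|---|
| 1% | 0.01 × 15.3 = 0.15 |
| 2% | 0.02 × 15.3 = 0.31 |
| 3% | 0.03 × 15.3 = 0.46 |
| 5% | 0.05 × 15.3 = 0.77 |

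The shift reaches 1 unit at p = 1/15.3 = 6.5%. It scales in proportion to the average improvement, so a smaller average improvement in this trial would give a smaller shift.

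**Step 5. Compare with the precision.** With 500 × 0.9 = 450 men and no stratification, the half-width is 1.96 × 8.5/√450 = 0.79. At p = 5% the shift is about as large as that half-width.

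**The plan's sample size.** The simple one-mean formula gives (1.96 × 8.5/1)² = 277.6, so 278, and 278/0.9 = 308.9, so 309. This does not reproduce 500. The stratum sizes used are not given and 500 is worded as a ceiling. Nothing in this point depends on it.

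**Returned-form route.** No size can be derived, because the documents do not say how a catheterised man would score.

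**The case against.** The plan does not ignore catheters. It waives the form for the men concerned, removes men catheterised at the end of the procedure from the EAS, and limits the primary objective to men able to give a baseline score. The remaining group must be catheterised after the procedure, still be catheterised at 12 months, and have had no non-PAE BPH procedure, which would have ended their follow-up. That group may be small. The ±1 unit is a precision target rather than a success margin, and the plan sets no pass/fail threshold. Against a background improvement of about 15.3 points, a shift of 0.15 to 0.77 is 1% to 5%. All of this stands and limits the importance of the point.

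A reader might go further and infer that a catheterised man who returns the form will score near zero and count as a strong responder, so that the worst outcomes give the best scores. With a returned score of 0 to 6 against a baseline of 21.5, the credit would be 15.5 to 21.5 points, or 0.78 to 1.08 in the mean at 5%. The documents do not support that reading. Section 4 says only that the questions may not be relevant. The items and answer options are not reproduced, and such a man could report bother or skip items. That calculation also assumes that every catheterised man passes over the waiver and scores low.

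The waiver does not remove the problem, however. A man who uses it has a missing score, and 8.5.2.1 then gives him the average. That route needs no assumption about how he would have answered.

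**Conclusion.** The gap is real and worth closing, though modest in size. As written, the plan either counts a score whose relevance it doubts or credits a man with a catheter in place with an average improvement.

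- For a blank form the error favours PAE by about 0.15 points per 1% of analysed men and 0.77 at 5%. This rests on the background averages of 21.5 and 6.2, on no change as the fair value, and on an assumed 1% to 5%.
- For a returned form, neither direction nor size is established.
- The EAS as primary population is an inference from 8.4.1, because 8.5.2 names none. Section 8.5.1.7 places secondary endpoints on the FAS, which has no catheter screen, while 8.5.3.1 uses the EAS for IPSS over time. These sections should be reconciled.

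The documents give no ground for saying that the primary conclusion would reverse.

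**What to change.** 1. In 8.5.2, 8.5.2.1 and 8.5.3.1, state that an IPSS completed while an indwelling catheter is in place at that visit is not used as a valid score. Include forms returned by mail or email, which section 6.5 allows.
2. In the same sections, state that these men are not given the age-specific average. Voiding the score without this step would send them into the imputation and leave the 15.3-point credit in place.
3. Add a pre-specified sensitivity analysis that sets their change from baseline to 0. This is needed as well as steps 1 and 2: leaving these men out gives a mean for men without a catheter, which is numerically close to average imputation. Only the analysis with change set to 0 shows the effect.
4. Report the number of such men beside the 12- and 24-month IPSS results. This replaces the assumed 1% to 5% with a count.

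The cost is SAP wording and one further analysis. Catheter use is already recorded at each IPSS visit, so no new data are needed. The downside is that the estimated improvement may be slightly less favourable.

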## 5 Eligibility Criteria

- Inclusion Criteria
  - Patient has signed informed consent
  - Patient age is 18 years or older at time of informed consent
  - Patient will undergo PAE with Embosphere Microspheres for the treatment of symptomatic BPH with LUTS
- Exclusion Criteria
  - Patient is unable or unwilling to provide follow-up information
  - Patient is undergoing PAE for reasons that do not include symptomatic BPH with LUTS
  - Any other reason the investigator deems cause for exclusion

## 6 Visit schedule and actions

### 6.1 Baseline Visit

The following baseline data will be collected:

- Date patient signs informed consent
- Demographics
- Prior BPH procedures
- Current Medication for BPH (5 $\alpha$ -Reductase inhibitors,  $\alpha$ -blockers, ED medications, OTC medications, etc.)

The following baseline data will be collected within 4 weeks of the study PAE procedure:

- International Prostate Symptom Score (IPSS)
  - Must be self-administered by patient
- Sexual Health Inventory for Men (SHIM)
  - Must be self-administered by patient

The following baseline data will be collected within a timeframe consistent with standard of care:

- Prostate Size Assessment
- Urinary Evaluations (Indwelling urinary catheter use, Maximum urine flow rate (Qmax), and Post void residual volume (PVR)), if done
- Prostate specific antigen (PSA), if done

The following baseline data will be collected within 12 months of the study PAE procedure:

- Prostate Biopsy, if done

## **6.2 Prostatic Artery Embolization (PAE) Procedure Information**

The following procedural data will be collected:

- Date of procedure
- Date and time of discharge
- Embolization start and end time
- Access site (Femoral/Radial)
- Was the PErFecTED technique used? (If yes, prostate lobe(s) used on)
- Was Foley catheter with contrast used?
- Lobes embolized (Right/Left/Both)
- Size of Embosphere Microspheres
- Total Volume Administered
- Device or Procedure-related adverse events

Patients will be given a form on which to record Device or Procedure-related adverse events during the first month post procedure.

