## **6.3 Visit 1: 4 Weeks ( $\pm 1$ week) Follow-Up**

The following information will be collected:

- Device or Procedure-related adverse events
- Changes in indwelling urinary catheter use
- BPH related medications
- Additional prostate procedures and/or imaging
- Prostate specific antigen (PSA), if done

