## 9 Device or Procedure-Related Adverse Events

A Device or Procedure-related adverse event is defined in this post market study as any event that began on or after the date of the PAE procedure and is considered related to the study procedure and/or device by the investigator. All related events must be reported in the case report form and followed until resolution.

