### 9.2 Relationship of Adverse Event to Device and/or Procedure

The Investigator, based on his/her clinical judgment and the following definitions, must determine the relationship of the adverse event to the device and/or procedure:

- Possible: The AE/SAE follows a reasonable temporal sequence from the time of study procedure, and/or follows a known response pattern to the study procedure but could have been produced by other factors.
- Probable: The AE/SAE follows a reasonable temporal sequence from the time of study procedure, follows a known response pattern to the study procedure, and cannot reasonably have been produced by other factors.
- Definite: The AE/SAE follows a reasonable temporal sequence from the time of study procedure; follows a known response pattern to the study procedure; and cannot have been produced by other factors.

[figure not shown]

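### The first-month patient form is described as covering related events only, so patients screen for cause before the investigator does and related events may be under-counted

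*Combined protocol and SAP*

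**What the plan says.** All references are to the combined protocol and SAP.

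- **Patient form.** Section 6.2: "Patients will be given a form on which to record Device or Procedure-related adverse events during the first month post procedure". No section tells the patient to write down every symptom or medical event.
- **Who judges cause.** Section 9 defines a reportable event as one "considered related to the study procedure and/or device by the investigator". Section 9.2 says that the investigator, using clinical judgement and set definitions, "must determine the relationship of the adverse event to the device and/or procedure".
- **Threshold for related.** The lowest category in the readable text of 9.2 begins: "Possible: The AE/SAE follows a reasonable temporal sequence from the time of study procedure". It still applies when other causes could explain the event.
- **Visits.** Section 4: "Safety will be assessed by evaluating device and procedure-related adverse events at the same time points, plus at 4 weeks following embolization". At 4 weeks, section 6.3 lists device or procedure-related events and, separately, "Changes in indwelling urinary catheter use", BPH medications and "Additional prostate procedures and/or imaging".
- **Mode of contact.** The text introducing Table 1 (section 6.6) allows follow-up in person, by telephone or by post, and by email or text if the patient has agreed.
- **Use of the data.** Section 8.1.2 makes the device or procedure-related event rate a secondary endpoint (post-procedure, 3, 12 and 24 months). Section 8.5.4 summarises the related events that were collected.

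**The concern.** The investigator's threshold is low, and he or she is expected to apply it with clinical knowledge. The form, as described, puts a lay screen in front of it. A patient who sees another explanation for a symptom has no reason to enter it, yet that is the kind of event that 9.2 would still class as Possible.

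Section 18 lists several risks that a layman could easily put down to something else. They include constipation, urinary infection, blood in the stool, a delayed rash, and urinary frequency or urgency in a man who already has LUTS.

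What is at stake is the related-event rate. Section 3.2 names device-related and procedure-related events as secondary objectives, and long-term safety is half of the goal stated in section 2. The study has one arm, so the absolute rate is the result, and no comparator shares any under-capture. Events missed in the first month would be missing from the 3-month figure and from every cumulative summary after it.

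**Working it through.** The plan gives no figure for event capture, so there is none to reproduce. The check is a comparison of the text: for each route by which a first-month complication could reach the case report form, does the route work whatever the patient believes about cause?

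| Route | Where | Independent of the patient's view of cause? |
|---|---|---|
| Patient form, month 1 | 6.2 | No, as described: related events only |
| Adverse event item at 4 weeks | 4, 6.3 | Not clearly: same restriction, and contact may be remote |
| Adverse event item at 3, 12 and 24 months and unscheduled visits | 6.4, Table 1 | Not clearly: same restriction |
| Catheter changes, BPH medications, further prostate procedures or imaging at 4 weeks | 6.3 | Yes, but limited to urinary and prostate matters |
| Serious event reporting | 9.4 | The 24-hour clock starts when the site learns of the event |
| Monitoring of source documents | 16, 17 | Partly: it verifies recorded data and sees only what is in the records |
| Independent safety medical monitor | 18 | No: the examples given are treatment-related events and deaths, so a non-fatal event that was not reported would not normally arrive |

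Two things follow.

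1. Several routes exist besides the form, and one of them (catheter, medication, procedure and imaging data) does not depend on attribution. It could expose retention or a repeat procedure. It would not directly expose rectal bleeding, a skin change, constipation or an access-site problem.
2. No section requires the site to ask about all symptoms before relatedness is assigned. An investigator may do so, but the plan does not ensure it.

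**Direction and size.** Let r be the share of truly related first-month events that patients recognise as related, and v the share of the remainder that the visits recover. The proportion missed is

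(1 − r) × (1 − v).

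This cannot be negative, so this mechanism can only lower the count. Neither r nor v is in the documents. Purely as an assumption, take r between 0.70 and 0.90:

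- v = 1 (full recovery): 0.30 × 0 = 0 and 0.10 × 0 = 0, so nothing is missed.
- v = 0.5: 0.30 × 0.5 = 0.15 and 0.10 × 0.5 = 0.05, so 5% to 15% is missed.
- v = 0 (no recovery): 0.30 and 0.10, so 10% to 30% is missed.

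The spread from 0% to 30% comes entirely from the assumed values. It shows only that the answer depends on what the visit elicits, which the plan leaves open. It is not an estimate for this study.

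**The case against.** The case on the other side is substantial.

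- **The form has not been seen.** Device or procedure-related adverse event is the protocol's standing label for its safety data, used in sections 6.2 to 6.4, 8.1.2 and 9. Section 6.2 may just be using that label for what is in fact an open diary or a symptom checklist. What men are told at consent about likely complications is also unknown. This stands, and it limits the point to the plan as written.
- **The form is not the only route.** A reader might infer that unrecognised complications never reach the site, or that the form is the sole record of the first month. The documents do not support either inference: events are also collected at 4 weeks, at later visits and at unscheduled visits, and some items are collected regardless of cause.
- **The formal decision is unchanged.** A reader might also infer that patients take over the causality decision. They do not. Sections 9 and 9.2 leave it with the investigator, and nothing ties the investigator to the form or limits Visit 1 to its entries. Patients make a first screen at most.
- **No endpoint is read off the form.** Section 8.1.2 reports rates at post-procedure, 3, 12 and 24 months, so a first-month event elicited later still counts. This stands, and it is why a form-only capture figure would not measure the bias in any planned result.
- **Collecting related events only is a deliberate choice** in a post-market study. That is acceptable, and the fix leaves it alone.

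What these arguments do not answer is that the main back-up, the visit adverse event item, is described with the same restriction and may be completed remotely.

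**Conclusion.** The point holds in a limited form. As section 6.2 is written, patients pre-screen for cause before the investigator's assessment under 9 and 9.2. Complications that they do not link to PAE may be under-reported, and the visits only partly correct this. Any resulting bias in the related adverse event rate is downward. Its size cannot be derived from the documents.

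The conclusion assumes that the form's wording follows the description in 6.2, and that sites do not already ask about all symptoms as routine. If either assumption is wrong, the problem shrinks to aligning the protocol text with practice. The primary endpoint and the sample size are not affected. This is a cheap improvement, not a flaw that threatens the study.

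**What to change.** In sections 6.2 and 6.3, state that:

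1. the first-month form and the Visit 1 contact record any new or worse symptom and any unplanned medical contact, whatever the patient thinks caused it;
2. the investigator reviews every entry and assigns relatedness under 9.2;
3. only events judged related go to the adverse event page.

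The adverse event definition in section 9 and the endpoints in 8.1.2 stay as they are. If the existing form already asks openly, only the description in 6.2 and the Visit 1 instruction need to change.

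Cost: revised form wording with IRB/EC notification, a few minutes of triage per patient at Visit 1, and possibly slightly higher reported adverse event rates. If the change comes after some men have completed the first month, the report should say which form each patient used, because capture may differ between the two.
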